**Model Specifications**

Several of the specific analyses shown in Table 7-2 involve estimating models. Table 7-3 provides the detailed specifications for these models. The first four models – the breastfeeding decision model, the formula supplementation model, the breastfeeding cessation model, and introduction of other foods model -- mirror models used in the previous IFPS-1 study. Initially, we will estimate these models primarily using the covariates that were used in the IFPS-1 study. This will facilitate the comparisons to the past research. We will also explore extending this work by making some improvements in the measurement of variables, the estimation method, and the covariates used. For these models, the additional covariates and estimation methods we propose to explore are noted in italics on Table 7-3. For many of the explanatory variables there are alternative proxy variables that we could use to measure the concept we are trying to capture. We will explore these alternative proxies if the initial variable proves to be insignificant. The weight and growth models shown in Table 7-3 are new.

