It should be noted that ultimately the variation in service delivery we observe between sites will determine which factors to include in our composite measures as well as whether the final measures are effective in capturing meaningful program variation that can be related to policies. Therefore, to some extent this work will be exploratory and we will assess alternative composites. For example, if we find the quality of sites’ educational programs vary by phase we will consider having separate composites for newborn feeding, infant feeding transition, and toddler feeding. In contrast, if sites that deliver effective newborn feeding education, almost always also deliver strong infant feeding transition and toddler feeding programs, a single education composite will suffice.

---

The WIC program variables will be composite measures. A composite measure is a combined metric that incorporates multiple individual measures to provide a single score. It is used as a way to measure concepts that are too complex to be measured simply with one item. Composite measures are also a data reduction technique used to avoid having many highly correlated variables in the same analyses which creates statistical challenges. The five WIC program variables will be composite measures of the component variables listed in the Research Plan and are intended to capture different aspects of how the program is being delivered and experienced. For each of the five composite measures, we will develop weights for the component variables and combine them into a single score (index variable). A simple approach for doing this is to take a straight average of all the component variables but this approach would not address the differing importance of the component items or their correlation with each other. We propose to use factor analysis (a statistical technique) to determine the relative weights to use in the creating the composite measure.

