**Table 7-3. Proposed model specifications**

Model	Dependent variable	Estimation methods	Minimum covariates to explore
Breastfeeding decision	
 
■ Initiating breastfeeding
 
■ Breastfeeding at hospital discharge
 
 Measured dichotomously and categorically (all breastfeeding, combination, all formula)	
 
■ Logistic regression (dichotomous)
 
■ Multinomial logistic regression (categorical)
 
	
 
■ Socio-demographics: Age, race/ethnicity, born in US, father in house, infant first born, income, poverty level, education, worked during pregnancy
 
■ Maternal and infant health: Mother's post-delivery health status, infants health status (measured as in NICU or more than 6 weeks premature or very low birth weight)
 
■ Prenatal attitudes, beliefs and knowledge: Perceived benefits of breastfeeding, perceived barriers, breastfeeding intentions
 
■ Prenatal experience and advice: breastfed previous children, receipt of advice to breastfeed from physician, receipt of advice to breastfeed from family, receipt of breastfeeding information from non-WIC sources
 
■ WIC program experience: Education, peer counseling, time in WIC
 
■ Hospital experience: Mom's length of stay, baby's length of stay, receipt of formula or bottle in gift package, had baby friendly practices
 

Table 7-3. Proposed model specifications (continued)

Model	Dependent variable	Estimation methods	Minimum covariates to explore

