Growth	
 
■ Repeated measures of child's weight/length
 
	
 
■ Growth model
 
	
 
■ Socio-demographics: Gender, race/ethnicity, income Maternal/family health: Maternal BMI, paternal obesity, maternal diabetes, smoking during pregnancy
 
■ WIC program experience: Education, food package, time in WIC
 
■ Child's health and physical activity: Birth weight, premature
 
■ Basic dietary intake: Breastfeeding duration
 

We will estimate several variants of the breastfeeding decision model. First, we will use two alternatives for the dependent variable: initiating breastfeeding and breastfeeding at hospital discharge. Similarly, we will explore using dichotomous measures (yes, no) for these variables as well using categorical measures that capture mixing breastfeeding and formula feeding from the start. Additionally, we will have mother's prenatal attitudes collected prior to delivery (rather than retrospectively) and can also explore how their breastfeeding intentions for initiation and duration affect actual initiation and exclusivity. Finally, for this model we will explore the viability of using a summary index to capture the mother's attitudes, beliefs, and knowledge on breastfeeding and her hospital experience in place of the individual covariates in these groups.

Our estimates of the formula supplementation model and time until the introduction of other foods models will closely parallel the past work with few extensions. In estimating the formula supplementation model we will explore how breastfeeding intentions regarding duration (which is typically not collected) affect the time until formula supplementation. The covariates we will examine for predicting the time until breastfeeding cessation and the introduction of cereals, fruits, and vegetables will parallel those used in the IFPS-1 study.

For the new weight model, we will run separate models estimating weight/length for the children at 6, 12, and 24 months. In addition to including direct measures of toddler feeding practices (such as family has a clean plate policy), we will explore the viability of using summary measures of a range of toddler feeding practices to predict weight outcomes.

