Finally, in all these models we will capture the cross-sectional variation in the WIC program experience through the inclusion of WIC program composite measures which will be an enhancement over past studies. For breastfeeding initiation and duration decisions, we expect that the variation in educational programs, peer counseling and the provision and support for breast pumps will be factors affecting individuals' decision. For infant feeding transitions and toddler weight outcomes, we expect that variation in education and the food packages will be important factors. For all of these decisions and outcomes, we expect that the time the mother has spent in WIC will be an important predictor.

This page left intentionally blank

Table 8-1 provides a summary of our proposed analytical report schedule and the content of each report. There are a few topic areas that draw solely from data collected during the first few interviews and these analyses can be completed prior to finishing all the data collection. Analyses of prenatal views, the study design and sample, breastfeeding decisions, hospital practices and neonatal circumstances, and breastfeeding problems can be completed prior to conducting the 13 months interview. Additionally, the analyses on formula supplementation, breastfeeding and formula feeding practice, and the continuation and cessation of breastfeeding can be completed using data through the month 13 interview. The analyses of all the other topic areas at least partially depend on data collected from later interviews. Therefore, as our report schedule shows, there are some topics for which we will provide preliminary analysis based on the currently available data and then update these analyses in final infant and final infant and toddler reports. Please note, that while we are contracted to deliver 4 interim reports on the toddler interviews, since FNS eliminated the 21 month interview, we have only 3 data collection interviews. We have some suggestions for the content of the 4th report we would like to discuss with FNS.

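### Alternative proxies are tried only when the first variable is non-significant, with no commitment to report them all, so a concept's false-positive rate can exceed nominal

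*Combined protocol and SAP*

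**What the plan says.** Section 7.5, under Model Specifications, describes the starting point for the four models that mirror IFPS-1 (breastfeeding decision, formula supplementation, breastfeeding cessation, introduction of other foods): "Initially, we will estimate these models primarily using the covariates that were used in the IFPS-1 study". It then announces improvements in measurement, estimation method and covariates, and adds: "For many of the explanatory variables there are alternative proxy variables that we could use to measure the concept we are trying to capture". The next sentence gives the rule for using those proxies: "We will explore these alternative proxies if the initial variable proves to be insignificant".

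Table 7-3 lists covariates for each model under the column heading "Minimum covariates to explore", so the list is a floor and not a closed set.

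Other re-measurement is planned without a stated link to significance. After Table 7-3 the plan will "explore the viability of using a summary index to capture" attitudes and hospital experience. Section 7.2 (WIC Program Variables) says of the program composites that "the variation in service delivery we observe between sites will determine which factors to include in our composite measures", and that "to some extent this work will be exploratory and we will assess alternative composites". The closing paragraph of Section 7.5 says that "in all these models we will capture the cross-sectional variation in the WIC program experience through the inclusion of WIC program composite measures".

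**The concern.** A significance result on the outcome model decides whether further measures of the same concept are examined, and the rule works in one direction only. A significant first variable is left alone, while a non-significant one gets further chances. The plan does not name the proxies, cap their number, say which version is final, or commit to listing what was tried.

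This matters because Section 7.3 presents these regressions as the causal analyses. Table B-1, question 22, relies on them to say which program and non-program factors contribute to breastfeeding initiation, formula supplementation and the introduction of foods. If a concept appears as a predictor after an undisclosed search, the p-value beside it does not have its stated error rate. A reader cannot tell whether a given coefficient is the first measure tried or the one that worked.

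**Working it through.** **Inputs**

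- Rule: further proxies are examined only after a non-significant first variable (Section 7.5).
- Number of proxies per concept: not stated. Assumed one or two, so k = 2 or 3 variables tried in total.
- Significance level for model coefficients: not stated. The levels 0.05 and 0.01 appear only in the chi-square footnotes of the Appendix C table shells. Both are used here as assumptions, two-sided.
- Correlation between the proxies' test statistics: not stated. Section 7.2 expects many variables within covariate groups to be correlated but gives no value. Assumed range 0 to 0.95.
- Condition: a concept counts as significant if any proxy tried is significant. The plan does not say this; the calculation shows the consequence if it happens.

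The plan gives no error rate for these models, so there is no figure of its own to reproduce.

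**Reduction.** Testing the first variable, trying the others only if it fails, and accepting any success is the same event as at least one of the k variables being significant. No separate formula for the sequential order is needed.

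**Formula.** Take equicorrelated standard normal statistics with correlation ρ and critical value c. Given the common factor g, each statistic stays inside ±c with probability

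p(g) = Φ((c − √ρ·g)/√(1−ρ)) − Φ((−c − √ρ·g)/√(1−ρ)),

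and P(any significant) = 1 − ∫ p(g)^k φ(g) dg, evaluated numerically. At ρ = 0 this becomes 1 − (1 − α)^k:

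- α = 0.05: 1 − 0.95² = 9.75%; 1 − 0.95³ = 14.26%.
- α = 0.01: 1 − 0.99² = 1.99%; 1 − 0.99³ = 2.97%.

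**Results: chance of declaring a null concept significant**

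| α (two-sided) | Alternatives | ρ = 0.95 | 0.9 | 0.8 | 0.5 | 0 |
|---|---|---|---|---|---|---|
| 0.05 | 1 | 6.46% | 7.04% | 7.81% | 9.07% | 9.75% |
| 0.05 | 2 | 7.34% | 8.36% | 9.82% | 12.54% | 14.26% |
| 0.01 | 1 | 1.36% | 1.49% | 1.66% | 1.90% | 1.99% |
| 0.01 | 2 | 1.58% | 1.84% | 2.18% | 2.73% | 2.97% |

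At ρ = 1 the rate returns to nominal.

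**Check of the sequential rule by simulation** (1,000,000 draws per setting, α = 0.05). With three variables at ρ = 0.7, simulation gives 10.93% against 10.92% by integration. With three at ρ = 0.9, it gives 8.37% against 8.36%. The first variable alone rejects at about 5.0% in each case, which confirms that its own error rate is untouched.

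**What the plan commits to reporting.** Table 7-2 lists the planned tables and figures by title. Initiation, formula supplementation and cessation each have one table of model estimates, and initiation also has a figure of relative odds by information source. No title compares proxies or sets the IFPS-1-covariate fit beside later versions. Table A-1 says of the initiation model that content will be similar but the models will differ.

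**The case against.** The strongest reply is that the harm depends on a step the plan does not state. It says proxies will be explored. It does not say that a significant proxy replaces the initial variable or makes the concept count. On that reading there is only a missing disclosure rule. This is correct as far as it goes, and it is why the inflation is stated conditionally. It does not remove the problem, because the text as written permits either practice and commits to neither.

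Second, zero correlation is implausible for variables chosen to measure one concept, and Section 7.2 itself expects correlation. That stands: the independent-test figures are an upper illustration and the high-correlation values may be closer. At ρ of 0.9 to 0.95 with one alternative, the rate is 6.5% to 7.0% against an assumed 5%.

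Third, the initial fit is meant for comparison with IFPS-1, which is a primary objective, so it may well be shown. That is a reasonable expectation and a partial anchor, but not a promise. The Table A-1 remark that models will differ is weak contrary evidence, since announced extensions already explain it.

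Fourth, much of the modelling is worded as exploratory. The label in Section 7.2 concerns the WIC composites and does not govern the proxy rule, and Section 7.3 still uses the models for causal questions. The rule's reach to the composites is inferred from the closing paragraph of Section 7.5; the plan neither states nor excludes it. The criterion for judging the summary index viable is also unstated, so that choice too could be influenced by model results.

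Finally, one could ask only for disclosure of the proxies tried. That would cure the reader's problem but leave a one-sided trigger in the plan.

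**Conclusion.** The concern holds. The plan makes non-significance the trigger for trying other measures of a concept, has no counterpart for significant results, and gives no commitment to report every proxy or allow for the search. If any significant proxy counts, the per-concept false-positive rate exceeds nominal for any number of alternatives, unless the test statistics are perfectly correlated.

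The direction does not depend on the assumed inputs, but the size does. At an assumed two-sided 0.05, the rate is 6.5% to 9.8% with one alternative and 7.3% to 14.3% with two. At an assumed 0.01, it is 1.4% to 2.0% and 1.6% to 3.0%. If the initial variable is always reported and only its p-value is used for the claim, the nominal rate is kept.

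The rule covers at least the four models that mirror IFPS-1. The absence of a reporting commitment is judged on this document alone; the separate deliverables it cites were not available. This should be fixed before the models are fitted.

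**What to change.** In the Model Specifications text of Section 7.5:

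1. Delete the significance trigger.
2. Treat the IFPS-1 or Table 7-3 covariate as the lead measure of each concept. Where more than one measure is available, choose one without sight of its coefficient in the outcome model and record the choice.
3. Report the lead measure whatever its p-value, and show the initial IFPS-1-covariate fit beside any later version.
4. Fit any alternative proxies whether or not the lead measure is significant, report all of them, and label them sensitivity or exploratory analyses.

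Most lead measures are already named in Table 7-3 or IFPS-1 and no new data are needed. The cost is the change of wording plus extra fitting and tabulation, which grows with the number of variables that have proxies. Fewer predictors may be reported as significant, and a poorly measured lead variable may stay in the main model with its better alternative shown only as a sensitivity analysis.

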**Table 7-3. Proposed model specifications**

Model	Dependent variable	Estimation methods	Minimum covariates to explore
Breastfeeding decision	
 
■ Initiating breastfeeding
 
■ Breastfeeding at hospital discharge
 
 Measured dichotomously and categorically (all breastfeeding, combination, all formula)	
 
■ Logistic regression (dichotomous)
 
■ Multinomial logistic regression (categorical)
 
	
 
■ Socio-demographics: Age, race/ethnicity, born in US, father in house, infant first born, income, poverty level, education, worked during pregnancy
 
■ Maternal and infant health: Mother's post-delivery health status, infants health status (measured as in NICU or more than 6 weeks premature or very low birth weight)
 
■ Prenatal attitudes, beliefs and knowledge: Perceived benefits of breastfeeding, perceived barriers, breastfeeding intentions
 
■ Prenatal experience and advice: breastfed previous children, receipt of advice to breastfeed from physician, receipt of advice to breastfeed from family, receipt of breastfeeding information from non-WIC sources
 
■ WIC program experience: Education, peer counseling, time in WIC
 
■ Hospital experience: Mom's length of stay, baby's length of stay, receipt of formula or bottle in gift package, had baby friendly practices
 

Table 7-3. Proposed model specifications (continued)

Model	Dependent variable	Estimation methods	Minimum covariates to explore
Formula Supplementation	
 
■ Time until formula supplementation
 
	
 
■ Survival analysis
 
	
 
■ Socio-demographics: Age, race/ethnicity, born in US, infant first born, use of childcare, education, worked during pregnancy
 
■ Maternal and infant health: Mother's post-delivery health status, infants health status, birth weight, reported problems breastfeeding
 
■ Prenatal attitudes, beliefs and knowledge: Perceived benefits of breastfeeding, perceived barriers, how long intend to breastfeed
 
■ Prenatal experience and advice: Receipt of advice to breastfeed from physician, receipt of breastfeeding information from non-WIC sources
 
■ WIC program experience: Education, peer counseling, breast pumps, time in WIC
 

Breastfeeding cessation	
 
■ Time until cessation
 
	
 
■ Survival analysis
 
	
 
■ Socio-demographics: Age, race/ethnicity, born in US, infant first born, education, use of child care
 
■ Maternal health: Reported breastfeeding problems
 
■ Breastfeeding practices: Current use of formula
 
■ Prenatal attitudes, beliefs and knowledge: Perceived benefits of breastfeeding, perceived barriers, how long intend to breastfeed
 
■ Prenatal experience and advice: Receipt of advice to breastfeed from physician, receipt of breastfeeding information from non-WIC sources
 
■ WIC program experience: Education, peer counseling, breast pumps, time in WIC
 
■ Return to work/school: Returned to work/school within 2 months
 

Introduction of other foods	
 
■ Time until cereal
 
■ Time until fruits
 
■ Time until vegetables
 
■ Time until meats
 
	
 
■ Survival analysis
 
	
 
■ Socio-demographics: Age, race/ethnicity, born in US, household size, income, poverty level, use of child care, returned to work or school, education
 
■ Feeding practices: current use of formula
 
■ Attitudes, beliefs and knowledge: Belief formula provided from WIC is insufficient, parental assessment of baby's weight
 
■ Prenatal experience and advice: Receipt of breastfeeding information from non-WIC sources
 

Table 7-3. Proposed model specifications (continued)

Model	Dependent variable	Estimation methods	Minimum covariates to explore
			
 
■ WIC program experience: Education, time in WIC
 
■ Return to work/school: Returned to work/school within 2 months
 

Weight	
 
■ Child's weight/length (6, 12, and 24 months)
 
	
 
■ OLS
 
■ Quantile regression
 
	
 
■ Socio-demographics: Gender, race/ethnicity, income, born in US
 
■ Maternal/family health: Maternal BMI, paternal obesity, maternal diabetes, smoking during pregnancy, household food security (24 months only), maternal fruit and vegetable dietary intake (24 months only)
 
■ WIC program experience: Education, food package, time in WIC (and peer counseling for 6 month weight/length)
 
■ Child's health and physical activity: birth weight, premature, rapid early weight gain, physical activity indoors, physical outdoors (for 24 month measure) current sleep duration
 
■ Basic dietary intake: Breastfeeding duration, current intake of sweetened beverages
 
■ Feeding practices: Clean plate policy, track eating, careful not to feed too much
 

Growth	
 
■ Repeated measures of child's weight/length
 
	
 
■ Growth model
 
	
 
■ Socio-demographics: Gender, race/ethnicity, income Maternal/family health: Maternal BMI, paternal obesity, maternal diabetes, smoking during pregnancy
 
■ WIC program experience: Education, food package, time in WIC
 
■ Child's health and physical activity: Birth weight, premature
 
■ Basic dietary intake: Breastfeeding duration
 

We will estimate several variants of the breastfeeding decision model. First, we will use two alternatives for the dependent variable: initiating breastfeeding and breastfeeding at hospital discharge. Similarly, we will explore using dichotomous measures (yes, no) for these variables as well using categorical measures that capture mixing breastfeeding and formula feeding from the start. Additionally, we will have mother's prenatal attitudes collected prior to delivery (rather than retrospectively) and can also explore how their breastfeeding intentions for initiation and duration affect actual initiation and exclusivity. Finally, for this model we will explore the viability of using a summary index to capture the mother's attitudes, beliefs, and knowledge on breastfeeding and her hospital experience in place of the individual covariates in these groups.

Our estimates of the formula supplementation model and time until the introduction of other foods models will closely parallel the past work with few extensions. In estimating the formula supplementation model we will explore how breastfeeding intentions regarding duration (which is typically not collected) affect the time until formula supplementation. The covariates we will examine for predicting the time until breastfeeding cessation and the introduction of cereals, fruits, and vegetables will parallel those used in the IFPS-1 study.

For the new weight model, we will run separate models estimating weight/length for the children at 6, 12, and 24 months. In addition to including direct measures of toddler feeding practices (such as family has a clean plate policy), we will explore the viability of using summary measures of a range of toddler feeding practices to predict weight outcomes.

Finally, in all these models we will capture the cross-sectional variation in the WIC program experience through the inclusion of WIC program composite measures which will be an enhancement over past studies. For breastfeeding initiation and duration decisions, we expect that the variation in educational programs, peer counseling and the provision and support for breast pumps will be factors affecting individuals' decision. For infant feeding transitions and toddler weight outcomes, we expect that variation in education and the food packages will be important factors. For all of these decisions and outcomes, we expect that the time the mother has spent in WIC will be an important predictor.

This page left intentionally blank

Table 8-1 provides a summary of our proposed analytical report schedule and the content of each report. There are a few topic areas that draw solely from data collected during the first few interviews and these analyses can be completed prior to finishing all the data collection. Analyses of prenatal views, the study design and sample, breastfeeding decisions, hospital practices and neonatal circumstances, and breastfeeding problems can be completed prior to conducting the 13 months interview. Additionally, the analyses on formula supplementation, breastfeeding and formula feeding practice, and the continuation and cessation of breastfeeding can be completed using data through the month 13 interview. The analyses of all the other topic areas at least partially depend on data collected from later interviews. Therefore, as our report schedule shows, there are some topics for which we will provide preliminary analysis based on the currently available data and then update these analyses in final infant and final infant and toddler reports. Please note, that while we are contracted to deliver 4 interim reports on the toddler interviews, since FNS eliminated the 21 month interview, we have only 3 data collection interviews. We have some suggestions for the content of the 4th report we would like to discuss with FNS.

